After the informed consent form is signed, the screening tests are performed and the compliance with the inclusion / non-inclusion criteria is evaluated. The patient who passed the screening tests is enrolled in the study.¹

Clinical phase

Patients enrolled in the study receive Bioven at a dose of:

0.8-1.0 g / kg intravenously once a day for 2 consecutive days, the course dose is 1.6-2.0 g / kg. Allowed repeat course at same dosage in period 14-28 days from first infusion, if required.

The CRF records the time of administration of the study drug, the occurrence of possible adverse events.

Prescribed therapy and diagnostic results are recorded in the CRF based on the primary documentation.

Data are entered into the CRF according to the patient management plan.

Follow-up phase and completion of the study

This stage lasts for 4 weeks after the last administration of the drug (possible repeat course is not considered).

In all patients, the platelet count will be determined 48 hours after the start of the first administration of the study drug, on the 7th (\pm 1 day), 14th (\pm 2 days), 21st (\pm 3 days), 28th (+ 1-3 days) days after the start of therapy.

The results of the study are evaluated by endpoints.

Phase-by-phase breakdown and breakdown of visits are detailed in Section 6.4 "Tabulated schedule of events". Information is entered into the CRF after each visit, according to the "Schedule of study events".

The decision on any examinations and diagnostic procedures in routine clinical practice is made and controlled by professionals.

Blood sampling for platelet count is performed 6 times:

- at the screening phase;
- 48 (\pm 3) hours after the start of study drug administration;
- on the 7th (± 1) day from the start of study drug administration;
- on the 14th (± 2) day from the start of study drug administration;
- on the 21st (± 3) day from the start of study drug administration;
- on the 28th (+ 1-3) day from the start of study drug administration.

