Methods of descriptive statistics (for categorical variables – number and share in %, for quantitative variables – n, arithmetic mean, median, standard deviation, minimum and maximum), including plotting graphs and diagrams, interval estimation methods (plotting 95% confidence intervals for fractions and differences of fractions).

To assess the significance of the dynamics in the case of evaluating a parameter at two visits (before and after) in the case of quantitative variables, the Student's t test for paired data or Wilcoxon signed rank test will be applied depending on the results of checking the normality of the distribution of differences [after - before] using the Shapiro-Wilk test. To assess the dynamics of categorical variables, we will use the McNimar test or the test of homogeneity of

| Bioven | Page 15 |
|----------------------------|---------------------------------|
| Trial Code: 2021-BV-ITP-BP | Version 1.4 from July 03, 2023, |

marginal frequencies depending on the number of categories. To evaluate the statistical significance of differences in categorical variables in unrelated groups, we will use Pearson's chi-squared test or Fisher's exact test (depending on the frequency distribution in Table 2 * 2).

To assess the dynamics in the case of measuring variables at more than two visits, methods of univariate variance analysis (Anova) will be used, followed by contrast analysis (simple contrasts) or a posteriori analysis using the Tukey's test. Covariance analysis (ANCOVA) will be used to compare the variables for which the data were inhomogeneous in the initial state. To check the prerequisites for applying variance and covariance analysis, the normality of the distribution of data and their balances will be checked using the Shapiro-Wilk test. If the balances are not distributed normally, or if the data does not pass the normality check, the corresponding rank analysis will be performed. For the Shapiro-Wilk test, the significance level will be 0.01, and for other criteria – 0.05. If the effect of multiple comparisons occurs, the significance level adjustment will be applied using the Holm method or the Benjamini–Hochberg procedure.

Working with missing or incomplete data

Missed or incomplete data will be replaced using the Last-Observation-Carried-Forward (LOCF) method, or the method of enlarging intervals for series where the transfer of the last measurement is not applicable.

Conclusion on efficacy

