6.5.10 Blood sampling procedure

Blood samples for analysis will be taken on an empty stomach (8-10 hours after the last meal) from a vein with a disposable sterile syringe, catheter or vacutainer with asepsis/antiseptics. The blood is mixed with the anticoagulant (if required by the procedure for preparing the sample to obtain plasma) and in vitro on the day of blood collection is sent at room temperature to the central laboratory.

Blood volume:

- general blood test (erythrocytes, reticulocytes, hemoglobin, leukocytes and expanded leukocyte formula, platelet counting by the Fonio method- 4 ml;
- biochemical analysis of blood (ALT, AST, creatinine, urea, glucose, total bilirubin
- and its fractions) and determination of IgG levels in serum 10 ml;
- virological screening and antinuclear antibodies 5 ml;
- blood type and Rh factor up to 5 ml;
- Coombs test 4 ml;
- coagulogram 4 ml.

Blood volume by visits:

- at the screening stage 32 ml,
- on the 2nd visit 13 ml,
- on the 3rd visit 9 ml,
- on the 4th visit 9 ml,
- on the 5th visit 9 ml,
- on the 6th visit 23 ml.

1 additional blood sample (20 ml in total) is allowed.

| Bioven | Page 51 |
|----------------------------|--------------------------------|
| Trial Code: 2021-BV-ITP-BP | Version 1.4 from July 03, 2023 |

On other days of visits, blood sampling is provided to perform a general blood test. Each test requires 4 ml of blood. Additional blood sampling for a general blood test is performed one day after the visit, which showed a decrease in platelet count below 30×10^9 /l.

Patients may also have periodic general blood tests and / or biochemical blood tests. The amount of blood required for these tests is determined by the patient's condition and duration of treatment, and will be determined in fact, taking into account the non-harm to the patient.

If the sample was not taken according to the time scheduled by the protocol (missed), the labeled tube remains empty. Information explaining this event is entered into the CRF and primary documentation, and sampling continues at the scheduled time.

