8 EVALUATION OF EFFICIENCY

8.1 Primary efficacy endpoint:

Part (percent) of patients with response (R).

R is determined according to the following criteria:

- Patients with R: platelets count $> 30x10^{9}/L$ and at least a two-fold increase from the baseline count. This must be confirmed by at least 2 blood tests at least 7 days apart, and the absence of bleeding;

The primary efficacy variable is achievement of R during the study (yes/no).

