8.2 Secondary efficiency endpoints

Part (percent) of patients with a complete response (CR).

CR is determined according to the following criteria:

- Patients with CR: platelets count > 100 x 10^{9} /L, which is confirmed by 2 blood tests performed at least 7 days apart and the absence of bleeding;

Part (percent) of patients with no response (NR).

NR is determined according to the following criteria:

- Patients with NR: platelet count $< 30 \times 10^{9}$ /L or less than two-fold increase of baseline platelet count. This must be confirmed by at least 2 blood tests performed approximately 1 day apart, or the presence of bleeding;

Part (percent) of patients with loss of response (loss of R).

Loss R is determined according to the following criteria:

- Patients with loss R: a decrease platelet count < 30×10^9 /L or less than two-fold increase of baseline platelet count, or the occurrence of bleeding. Platelet counts confirmed at least 2 blood tests performed approximately 1 day apart.

Part (percent) of patients with loss of complete response (loss of CR).

CR loss is determined according to the following criteria:

- Patients with loss of CR: decrease platelet count < 100 x $10^9/L$, or the occurrence of bleeding. Platelet counts confirmed at least 2 blood tests performed approximately 1 day apart.

Time (in days) from treatment start to onset of a response (R); Time (in days) from treatment start to onset of a complete response (CR); Duration (in days) of response (R); Duration (in days) of complete response (CR);

Secondary efficacy endpoints are transformed into corresponding efficacy variables

Safety

- Frequency (percent) of adverse events

- Frequency (percent) of serious adverse events

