10.3.5. Significance level

The level of significance for the Shapiro-Wilk test is set at 0.01, and for other statistical tests at 0.05. In the case of the effect of multiple comparisons, the adjustment of the level of significance will be applied using the Holm method or the Benjamini-Hochberg method.

10.3.6. Work with missing or incomplete data.

Missing or incomplete data will be replaced using the Last-Observation-Carried-Forward (LOCF) method. Or by the method of enlarging the intervals for series where the transfer of the last measurement is not applicable.

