10.4. Data set for analysis

ITT (Intention-to-treat population) - all study participants who took the study drug at least once. Data from this sample will be used for safety analysis.

PP (Per Protocol) - all patients who met the requirements of the protocol. This population includes all patients who received protocol therapy in full, completed all scheduled visits, and had no significant protocol deviations. The data obtained on this sample will be used for analysis according to the criteria of drug effectiveness.

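### The plan does not prevent a carried-forward platelet count from acting as the 7-day confirmation of R or CR, because LOCF is the default and these endpoints are not exempted

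*Combined protocol and SAP*

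**What the plan says.** **Missing data.** Section 10.3.6 gives the general rule, "Missing or incomplete data will be replaced using the Last-Observation-Carried-Forward (LOCF) method", and then an alternative: "Or by the method of enlarging the intervals for series where the transfer of the last measurement is not applicable". The synopsis repeats the rule ("Missed or incomplete data will be replaced using the Last-Observation-Carried-Forward (LOCF) method"). Neither place names the series to which the alternative applies, and neither exempts an endpoint.

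**Endpoints.** For R (section 8.1) the platelet criterion carries the condition "This must be confirmed by at least 2 blood tests at least 7 days apart, and the absence of bleeding". For CR (section 8.2) the wording is "which is confirmed by 2 blood tests performed at least 7 days apart and the absence of bleeding". Section 10.3.3 makes both Yes/No variables. It does not say how to score a patient who has a qualifying count but no second one, or whether an imputed count can be the second one.

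**Schedule.** The synopsis says "Blood sampling for platelet count is performed 6 times": at screening, at 48 hours, and on Days 7, 14, 21 and 28. Section 6.5.10 foresees gaps: "If the sample was not taken according to the time scheduled by the protocol (missed), the labeled tube remains empty". Sampling then continues as scheduled.

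**Who is analysed for efficacy.** Section 10.4 uses the per-protocol set, meaning patients who, among other conditions, "completed all scheduled visits, and had no significant protocol deviations". Section 5.3 instead keeps in the efficacy analysis patients who drop out during follow-up after completing the drug, and says their lost data are not analysed.

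**The concern.** The confirmation requirement separates a response that lasts at least a week from a transient peak. LOCF assumes that the last value persists, which is the very thing the second test is meant to establish. If a carried-forward count may fill the second slot, a patient can be scored as a responder on observed data that do not meet the definition.

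The error for R and CR runs one way. Copying a qualifying count forward can turn an unconfirmed patient into Yes, and cannot turn a patient with two observed qualifying counts into No. R is the only variable behind the non-inferiority conclusion (section 10.3.7). The trial is open-label and single-arm, so the scoring convention should not be left to a choice made after the counts are known.

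**Working it through.** **1. The plan's own figure.** Section 10.2 uses p = p0 = 0.78, δ = −0.25, and 1.96 and 1.28 for the two normal quantiles:

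(1.96 + 1.28)² × 0.78 × 0.22 / 0.25² = 28.82, rounded up to 29. With 20% dropout, 29/0.8 = 36.25; the plan states 36. Section 4.1 gives a total of 40, so both sizes are used below.

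**2. Where a copied count can create a pair.** On nominal days:

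| Last observed count | Carried to | Apparent gap |
|---|---|---|
| 48 h (Day 2) | Day 7 | 5 days, not enough |
| 48 h (Day 2) | Day 14 (Day 7 also missing) | 12 days |
| Day 7 | Day 14 | 7 days |
| Day 14 | Day 21 | 7 days |
| Day 21 | Day 28 | 7 days |

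Take a patient with qualifying counts at 48 hours and Day 7 and none later. With the ±1 day window these are at most 6 days apart (Day 2 to Day 8), so R is unconfirmed. Filling Day 14 from Day 7 makes it Yes.

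**3. The decision threshold.** Section 10.1 gives the lower limit as (p − 0.78) − 1.96 × √[p(1−p)/n + 0.78 × 0.22/82], which must exceed −0.25.

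- 25/36: −0.0856 − 1.96 × 0.0894 = −0.261, fails.
- 26/36: −0.0578 − 1.96 × 0.0876 = −0.229, passes.
- The minimum to pass is 21/29, 26/36 or 28/40.

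One patient adds 1/36 = 2.8 points, or 1/40 = 2.5 points. Section 10.1 also prints a test that treats the literature rate as fixed. That moves the n=36 threshold to 25, but the result still turns on one patient.

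**4. False-claim chance.** Assumptions: true confirmed R is at the null, g = 0.78 − 0.25 = 0.53; a share f of patients has an initial qualifying count; a share d has no count after Day 7, independently of outcome. If LOCF confirms them, apparent R = g(1−d) + f·d. The false-claim chance is the exact binomial probability of reaching the threshold.

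| d | f | Apparent R | n=36 (≥26) | n=40 (≥28) |
|---|---|---|---|---|
| 0 | – | 53.0% | 1.5% | 2.2% |
| 5% | 70–90% | 53.9–54.9% | 1.9–2.5% | 2.8–3.7% |
| 20% | 80% | 58.4% | 6.3% | 9.1% |
| 20% | 70–90% | 56.4–60.4% | 3.8–9.9% | 5.6–14.0% |

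Only the 20% comes from the documents, as a dropout allowance. The values of f and the 5% are assumptions.

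**5. How the three handlings differ.** Illustration (assumed): 36 treated, 7 lost before confirmation, 21 of the 29 completers truly confirmed.

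- Lost patients scored No: 21/36 = 58.3%, lower limit −0.381, fails.
- Five of the 7 scored Yes by LOCF: 26/36 = 72.2%, lower limit −0.229, passes.
- The 7 excluded under section 10.4: 21/29 = 72.4%, lower limit −0.242, passes.

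The documents support more than one of these handlings, and they do not give the same answer.

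**The case against.** The strongest reply is that the endpoint text already settles the matter: it requires blood tests, and a copied value is not a blood test. On that reading a carried-forward count can never confirm R. This is sensible and may be what the sponsor intends, but the plan nowhere states it. What stands is that single-test scoring is permitted by silence and is not directed.

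A reader might infer that LOCF is mandatory for every missing value. The next sentence of section 10.3.6 excludes that. It does not close the gap, because it names no series and carrying forward is feasible for platelet counts.

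The exposure is also narrower than the 20% dropout figure suggests. Section 10.4 removes patients who miss visits, and section 5.3 says lost data are not analysed. A patient who attends every visit and lacks one sample will often have another observed pair at least 7 days apart. This stands, and it is why the 20% rows are conditional. Two routes stay open. Attending a visit does not guarantee a count: Visits 4 and 5 may be held by telephone or video with blood drawn elsewhere, and section 11.2 lists both major and minor schedule violations, so it is unclear whether one missed sample removes a patient from the per-protocol set. And section 5.3 expressly retains follow-up dropouts.

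Three further inferences are not supported:

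- That LOCF makes loss of response look better. Copying a low count would confirm NR or loss, which works against the drug, so the direction is not shown.
- That duration is left without censoring. Section 10.3.3 already applies Kaplan-Meier; only the censoring date is missing.
- That the clotting and haemolysis text covers platelet counts. It belongs to plasma preparation (section 6.5.11). Section 6.5.10 is the support for missed samples.

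**Conclusion.** The point holds as a gap in the primary-endpoint rule. LOCF is the default, R and CR are not exempted, and no rule makes an unconfirmed patient No. Sections 5.3, 10.3.6 and 10.4 conflict on follow-up dropouts: the first keeps the patients without their lost data, the second fills those data in, and the third leaves the patients out. The documents do not support saying that the plan prescribes response on a single count.

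On size, one wrongly confirmed patient is enough to change the result at the threshold. If the per-protocol set is applied strictly, the 5% case is the more realistic one and the effect on error is small: at n=36 it stays at about the nominal one-sided 2.5%, and at n=40 it reaches 2.8–3.7%. The 3.8–9.9% at n=36 requires that dropouts are retained and that all of the 20% lack counts after Day 7. If the patients without later counts were exactly the initial responders who had lost response, apparent R would be g + d and the chance at n=36 would be 5.7% (d = 5%) to 62.5% (d = 20%). That is an extreme bound, not an expectation.

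The sponsor should correct this before the data are analysed.

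**What to change.** In section 10.3.6 and the synopsis, state that:

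- platelet counts and bleeding status are not imputed for R, CR, NR, loss of R or loss of CR;
- R or CR is Yes only with two observed qualifying counts at least 7 days apart and the bleeding condition met, and any analysed patient without them is No;
- NR by count and loss by count also need two observed counts;
- Kaplan-Meier duration of R and CR is censored at the last observed count;
- LOCF for these endpoints is only a labelled sensitivity analysis.

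Reconcile sections 5.3, 10.3.6 and 10.4, so that one rule says whether follow-up dropouts are in the efficacy set and whether a missed sample at an attended visit removes a patient from it.

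**Cost.** The rules sit in the protocol, and section 11.2 counts changes that may affect statistical methods as significant, so this is a protocol amendment to the statistics section. No new data are needed. If few counts are missing, the stated response rate may be slightly lower. If the whole 20% allowance were lost before confirmation and retained as No, the loss would be large. With 36 treated, 7 lost and 78% confirmed among the 29 completers, the chance of reaching 26 is 9.2%, against 83.1% of reaching 21/29 if the 7 are excluded. The efficacy set and the scoring rule should therefore be settled together.

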6.3 Stage of follow-up and completion

The stage lasts from the last administration of the study drug and for 4 weeks.

The procedures are performed according to the schedule of procedures (Section 6.4, Table 1). If a decrease in platelet count $< 30 \times 109/L$ is detected, an additional blood test with platelet count by Fonio is performed one day after the visit.

Face-to-face or telephone/video visits are made to assess the patient's condition. The patient visits the blood collection point for laboratory testing. The investigator fills in all information about the patient's condition and examination results in the IRF.

| Bioven | |
|----------------------------|-------------|
| Trial Code: 2021-BV-ITP-BP | Version 1.2 |

6.4 Schedule of study procedures in tabular form Table 1. Schedule of study procedures.

| Visits | Visits 1 | Vi | sits 2 (госпіт | алізація) | Visits 3 | PLT control | Visits 4 | PLT control | Visits 5 | PLT control | Visits 6 | PLT contro |
|--|------------------------|-----------|----------------|-----------|-----------|----------------|-----------|----------------|-----------|----------------|-----------|---------------|
| Study stage | Screening ² | IMP admin | . IMP admin | Follow-up | Follow-up | every | Follow-up | every | Follow-up | every | Follow-up | every |
| Day relative to the first administration of the drug/Injection | Day (-14 -1) | Day 0 | Day +1 | Day +2 | Day +7 | day* | Day +14 | day* | Day +21 | day* | Day +28 | day* |
| Signing the Informed Consent Form | • | | | | | | | | | | | |
| Collection of demographics data | • | | | | | | | | | | | |
| Collection of anthropometric data, body weight ³ | • | • | • | | | | | | | | | |
| Collection of medical history ⁴ | • | | | | | | | | | | | |
| Objective physical examination 5 | • | • | • | • | • | | • | | • | | • | |
| Measurement of vital signs 6 | • | • | • | • | • | | • | | • | | • | |
| ECG in 12 leads; | • | | | | | | | | | | | |
| Coombs Direct Test (Antiglobulin Test)* | • | | | • | * | | * | | * | | • | |
| Determination of the level of total Ig G in the blood (g/l) | • | | | • | • | | • | | • | | • | |
| General blood test ⁷ | • | | | • | • | * | • | * | • | * | • | * |
| Biochemical blood test 8 | • | | | | | | | | | | • | |
| Blood test for blood group and Rh factor | • | | | | | | | | | | | |
| Coagulogram (PTI, APTT, fibrinogen) | • | | | | | | | | | | | |
| General urine analysis ⁹ | • | | | | | | | | | | | |

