9 SECURITY ASSESSMENT

9.1 Security endpoints

- Frequency of side effects;
- Frequency of serious side effects;
- Frequency of clinically significant changes in laboratory parameters and vital signs after infusion of the study drug;
- Dynamics of laboratory parameters.

9.2 Definitions concerning safety assessment.

Adverse event

Adverse event (AE) is any adverse change in the health of a patient or subject who has been administered a drug, regardless of the causal relationship with its use.

AE can be any adverse and unintentional change, symptom or disease, the time of occurrence of which does not exclude a causal relationship with the use of the drug, regardless of the presence or absence of a relationship with the use of the drug.

AEs may be abnormal laboratory parameters, first-time symptoms, or diseases that are related to the use of the drug, or if they existed before treatment of a condition whose severity or frequency increased after administration of the study drug.

Any medical condition present at the time of the patient's screening, but not deteriorating during the study, should not be recorded as an AE. However, if this medical condition worsens at any time during the study, it should be recorded as an AE.

Medical interventions, such as surgeries, diagnostic and treatment procedures, are not AEs, but they are interventions to treat the relevant medical condition and should be registered as a treatment for ANs.

Deviations from the norm of laboratory parameters

Any deviation from the norm of the laboratory indicator, which appeared for the first time, or the degree of severity, the frequency of which has increased compared to baseline, and meets at least one of the following criteria, must be recorded as AE:

- Requires medical intervention or diagnostic procedure;

- Leads to the cancellation of the study drug;
- Accompanied by complaints or symptoms, or causes them;
- Considered by the researcher as "clinically significant".

If there is any doubt as to whether a clinical event is an AE, it should be recorded as an AE.

Adverse reaction

Adverse reaction (AR) is an adverse reaction of the body associated with the use of a medicinal product (study drug), which implies the presence of at least a possible relationship with the use of a suspected drug (study drug).

During the study period, the investigator or study staff should conduct surveys and record information on adverse events / reactions as defined in this section of the protocol.

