10.3.4. Analysis of safety and tolerability parameters

A) Data on AE/AR, Indicators of descriptive statistics (frequency and part in percent) and a list of adverse reactions according to the MeDRA classification

B) Data on SAE. Indicators of descriptive statistics (frequency and part in percent) and a list of adverse reactions according to the MeDRA classification.

Clinically significant deviations in indicators characterizing the safety and tolerability of the drug: Laboratory results of general blood analysis, biochemical blood analysis and general urinalysis; the result of determining the Coombs test and signs of hemolysis.

Provide descriptive statistics for these indicators (n, arithmetic mean, median, standard deviation, minimum and maximum value) for all visits.

To evaluate the dynamics of laboratory indicators, we used the Student's test for paired data or the Wilcoxon signed rank test, depending on the normality of the distribution of paired differences ["after" - "before"]. Create dichotomous variables with the categories "normal" and "abnormal", calculate the indicators of descriptive statistics (frequency and part in %) for these variables.

Measurement results of heart rate, blood pressure, respiratory rate, body temperature. Indicators of descriptive statistics (n, arithmetic mean, median, standard deviation, minimum and maximum value) for each visit in accordance with the patient examination scheme. Evaluate the trend of changing these parameters.

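### The LOCF rule does not exempt safety data, so under Table 1 a missing Day 28 biochemistry value could be filled with the pre-dose screening value

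*Combined protocol and SAP*

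**What the plan says.** **Missing-data rule.** Section 10.3.6 reads "Missing or incomplete data will be replaced using the Last-Observation-Carried-Forward (LOCF) method". The synopsis repeats it: "Missed or incomplete data will be replaced using the Last-Observation-Carried-Forward (LOCF) method". Both add a fallback, a method of enlarging intervals, for series to which carrying forward does not apply. They do not define the method or name the series. Section 10.3.6 comes after both the efficacy plan (10.3.3) and the safety plan (10.3.4) and is limited to neither.

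**Laboratory safety analysis.** Section 9.1 lists as safety endpoints "Frequency of clinically significant changes in laboratory parameters and vital signs after infusion of the study drug" and "Dynamics of laboratory parameters". For these, 10.3.4 says: "To evaluate the dynamics of laboratory indicators, we used the Student's test for paired data or the Wilcoxon signed rank test". It also creates normal/abnormal variables and directs the analyst to "calculate the indicators of descriptive statistics (frequency and part in %) for these variables". It gives laboratory data no missing-data rule of their own. Section 10.4 defines a set of everyone dosed at least once and adds: "Data from this sample will be used for safety analysis".

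**Schedule.** In Table 1 (6.4) the row "Biochemical blood test 8" is marked at screening and Day 28 only. Section 6.6 also lists biochemistry at 48 hours, and the synopsis and 6.2 list it at Day 21.

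**Other rules that bear on this.**
- Section 5.3 keeps patients who leave during follow-up in the analyses, uses what can be evaluated, and leaves their missing data out.
- Section 5.3 also requires final-visit procedures after withdrawal for an adverse event.
- Section 6.5.10 foresees missed samples: the tube stays empty and the reason is recorded.
- Section 6.5.13 excludes laboratory results that are unsuitable for analysis.

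**The concern.** Carrying a value forward makes limited sense when the last value was also taken after treatment. Here, on the Table 1 schedule, the only earlier biochemistry value is the screening one. Using it as the Day 28 value records no change in a patient who was never measured after the infusion. That does not estimate a change after infusion, which is what 9.1 asks for.

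The rule also bears mainly on safety. The per-protocol efficacy set in 10.4 requires all scheduled visits to be completed, so filling in missed visits matters chiefly in the wider safety set. Creatinine is among the analytes, and section 2.4 names renal failure as a risk of IgG therapy. What is at stake is the accuracy of the laboratory change and abnormality tables.

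**Working it through.** The plan gives no figure on this point, so there is none to reproduce. The check has two parts.

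**1. Which value is carried?** The biochemistry row of Table 1 has 12 visit cells. Only the first (Day −14 to −1) and the eleventh (Day +28) are marked.

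| Samples actually drawn before Day 28 | Value carried to a missing Day 28 |
|---|---|
| Screening only (Table 1) | Screening, pre-dose |
| Also at 48 hours (6.6, Visit 2) | 48-hour value, post-dose |
| Also at Day 21 (synopsis, 6.2) | Day 21 value, post-dose |
| Also a periodic or unscheduled test (6.5.10, 6.6.1) or creatinine monitoring (2.4, untimed) after dosing | That value, post-dose |

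The blood volumes in 6.5.10 lean towards Table 1. The draws are blood count 4 ml, biochemistry with IgG 10 ml, virology and antinuclear antibodies 5 ml, blood group 5 ml, Coombs 4 ml and coagulogram 4 ml.
- Screening: 4 + 10 + 5 + 5 + 4 + 4 = 32 ml, as stated.
- Visit 2: blood count, Coombs and the 10 ml draw need 4 + 4 + 10 = 18 ml; 13 ml is allotted.
- Visit 5: blood count and the 10 ml draw need 4 + 10 = 14 ml; 9 ml is allotted.
- Visit 6: 23 ml is allotted, enough for 18 ml.

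This supports the Table 1 reading but does not prove it, because 6.5.10 also allows an additional sample.

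**2. How large is the effect where a screening value is carried?** Inputs: 40 patients (section 4.1). The number missing, m = 1, 2 or 4, is assumed.

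*Mean change.* Each filled patient contributes 0, so

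reported mean = [(40 − m) × observed mean + m × 0] / 40,

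and the ratio to the observed-case mean is (40 − m)/40.

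*Paired t.* Assume a mean change of 0.5 and an SD of 1 among the n = 40 − m observed.

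Observed cases: t = 0.5 × √n.

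With m zeros added, the mean is 0.5n/40 and the variance is [(n − 1) + 0.25n − 40 × (0.5n/40)²]/39.

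For m = 2: observed t = 0.5 × √38 = 3.08. After filling, the mean is 0.475, the variance is (37 + 9.5 − 9.025)/39 = 0.961, and t = 0.475/√(0.961/40) = 3.06.

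*Percent abnormal.* Assume 4 tested patients are abnormal and every carried value is normal. The observed rate is 4/(40 − m) and the reported rate is 4/40.

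| m | Mean-change ratio | t, observed → filled | % abnormal, observed → filled |
|---|---|---|---|
| 1 | 39/40 = 0.975 | 3.12 → 3.11 | 10.3 → 10.0 |
| 2 | 38/40 = 0.95 | 3.08 → 3.06 | 10.5 → 10.0 |
| 4 | 36/40 = 0.90 | 3.00 → 2.97 | 11.1 → 10.0 |

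The percent abnormal can also rise. Section 5.1 admits out-of-range values judged clinically insignificant, and a carried value of that kind would count as abnormal. The documents give no rate for this, so it is not sized. With nothing missing, every effect is nil.

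**The case against.** **The schedule is unsettled.** A reader might infer that the plan orders screening values into the Day 28 cell. The documents do not go that far. Section 6.6, the synopsis and 6.2 each call for a post-dose biochemistry sample. The Table 1 page carries a version 1.2 header among version 1.4 pages, and the row's footnote is not legible in the copy available. On the other side, 6.6 refers its 48-hour sample to the schedule of procedures, its Visit 5 list omits biochemistry, and the blood volumes fit Table 1. So a screening value could be carried, but it is not certain that one would be.

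**The fallback may apply.** A series with a single pre-dose value might be treated as one where carrying forward is not applicable. Because the term is undefined, it neither exempts such a series nor rules it out.

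**Section 5.3 can be reconciled.** A reader might see 5.3 and 10.3.6 as a plain contradiction. The specific rule for follow-up dropouts can reasonably be taken to govern the general one, although nothing says so. For the same reason, applying the planned 20% dropout to get a ratio of 32/40 = 0.80 is not supported: it fills in values that 5.3 leaves out. Patients withdrawn for adverse events should also have final-visit samples.

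**There is some laboratory-specific text.** Section 6.5.13 excludes unsuitable results and allows re-analysis of archived samples. That narrows the problem but does not reach a sample never drawn.

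**The consequence is slight.** This stands. The t statistic hardly moves, and section 9.2 has new or worsened laboratory deviations recorded as adverse events when judged clinically significant.

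**Conclusion.** The point holds in a conditional form. The LOCF rule does not exempt safety data. On the Table 1 schedule it could place a pre-dose value in the 'after' cell for a patient who remains in the study but has no Day 28 biochemistry. This assumes that no post-dose sample was drawn earlier and that the undefined fallback is not used.

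In that case the reported mean change is 0.975, 0.95 or 0.90 of the observed-case value for 1, 2 or 4 missing of 40. The missing counts, the 0.5 SD shift and the 4 abnormal patients are illustrative assumptions.

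A reader might infer that safety signals in general are diluted. They are not: the effect is confined to the laboratory tables and paired tests. Adverse event and serious adverse event counts and the primary endpoint are unaffected. Table 1 marks vital signs at every visit and Coombs also at Day 2, so a pre-dose carry would not normally arise there. Severity: minor.

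**What to change.** Add to 10.3.6 and to the matching synopsis paragraph:

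*Safety data are not imputed and are analysed as observed, with the number tested at each visit; a pre-dose value is never used as a post-dose value. For patients who drop out in follow-up, section 5.3 applies.*

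This resolves the point whichever biochemistry schedule is followed. No new analysis is needed, and reconciling Table 1 with the visit descriptions is a separate matter.

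The cost is two sentences in two places and slightly fewer pairs: 39, 38 or 36 instead of 40 in the illustration.
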